1.4 Lenalidomide Pharmacokinetics

Absorption:

Multiple dosing at the recommended dose-regimen does not result in drug accumulation.²⁰

In multiple myeloma patients, those with mild renal impairment had an AUC 56% greater than those with normal renal function.²¹

Distribution: In vitro (14C)-lenalidomide binding to plasma proteins is approximately 30%.²⁰

Metabolism and Excretion:

Steady-state levels are achieved by Day 4.²⁰

This drug is known to be substantially excreted by the kidneys, and the risk of toxic reactions to this drug may be greater in patients with impaired renal function.²² Dysuria, renal failure, hematuria, acute renal failure, azotemia, calculus ureteric, and renal mass are listed as reported adverse events in the package insert.

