1.7 Dosing Recommendation for Lenalidomide in Patients with Renal Impairment, Hemodialysis

Chen et al.²¹ conducted a multi-center study with lenalidomide 25 mg a day as a single oral dose in five groups of subjects defined by renal function [1] normal ($\text{CrCl} >80$ mL/min); [2] mild ($\text{CrCl}: >50- <80$ mL/min); [3] moderate ($\text{CrCl}: >30- <50$ mL/min); [4] severe ($\text{CrCl} <30$ mL/min but not on dialysis); [5] End Stage Renal Disease (requiring dialysis). Thirty subjects over the age of 35 were included in the study. Subjects with normal, mild, moderate or severe renal insufficiency received a single 25 mg oral dose of lenalidomide. Subjects with end stage renal disease (ESRD) received 2 single 25 mg doses, separated by 7-10 days: one dose on a non-dialysis day and the other dose 3 hours before a 4-hour hemodialysis.²¹ Blood and urine samples were collected over 72 hours and creatinine clearance was estimated with a 24-hour urine collection (Celgene Corporation 2006). Assessments included PK and safety parameters. All subjects completed the study. Total and renal clearance of lenalidomide were strongly correlated with CrCl ($R >0.9$, $p <0.01$). As a result, AUC_∞ increased with decreasing CrCl . The mean difference in AUC_∞ between normal renal function (NRF) and mild renal insufficiency (RI) was $<20\%$. Compared with the pooled data from NRF and mild RI groups, mean AUC_∞ increased approximately 140% in moderate RI, 240% in severe RI, and 360% in ESRD (off dialysis). There was no correlation between Cmax or Tmax and

CrCl. Approximately 10% of the dose was recovered in the dialysate of subjects with ESRD. Protein binding of lenalidomide was not markedly affected by RI (~35 - 44%). The drug was well tolerated. On the basis of these data, recommendations for initial starting doses were made.

The following dose recommendations were suggested by Chen et al. for patients with MM and MDS and renal dysfunction and were based on Area Under the Curve for entire exposure to the drug (AUC 0- ∞). The lower doses of lenalidomide recommended for patients with renal dysfunction are derived from modeling to produce AUCs comparable to those produced by the administration of a 25 mg or 10 mg dose of lenalidomide, respectively, in patients with normal renal function. (Note: For previously treated multiple myeloma dosing is for 21 days of a 28-day cycle. Dosing is continued or modified based on clinical and laboratory findings.)

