5. Bone marrow (with aspirate/FISH/cytogenetics) and skeletal survey may be used if performed ≤90 days of study enrollment.
6. Only applies to selected Mayo Clinic subjects registered to the Phase II component. Pharmacokinetics of lenalidomide: 5cc of blood is to be drawn and put into an EDTA tube at the following time points on Day 6 of Cycle 1: 0 (pre-dose), 0.5, 1, 1.5, 2, 3, 4, 6, 8, 24 hr at all dose groups and at 48 and 72 hr for patients in Group B with severe renal impairment or in Group C on dialysis (hemodialysis or peritoneal dialysis). Please see Section 14.2 for processing procedures. Pharmacokinetic samples will be collected from up to 12 Mayo Clinic participants with a minimum of two patients in each group (Groups A, B and C) of the Phase II component.
7. Treatment with Coumadin should be used with caution. If a patient is being treated with Coumadin, close monitoring of INR is required.
8. Pregnancy tests for females of childbearing potential. A female of childbearing potential (FCBP) is a sexually mature female who: 1) has not undergone a hysterectomy or bilateral oophorectomy; or 2) has not been naturally postmenopausal (amenorrhea following cancer

therapy does not rule out childbearing potential) for at least 24 consecutive months (e.g., has had menses at any time in the preceding 24 consecutive months). Pregnancy tests must occur within 10–14 days prior to initiation of Cycle 1 of lenalidomide and again within 24 hours prior to initiation of Cycle 1 of lenalidomide. FCBP with regular or no menstruation must have a pregnancy test weekly for the first 28 days and then every 28 days while on lenalidomide therapy (including breaks in therapy); at discontinuation of lenalidomide and at Day 28 post the last dose of lenalidomide. Females with irregular menstruation must have a pregnancy test weekly for the first 28 days and then every 14 days while on lenalidomide therapy (including breaks in therapy), at discontinuation of lenalidomide and at Day 14 and Day 28 post the last dose of lenalidomide (see Appendix V: Risks of Fetal Exposure, Pregnancy Testing Guidelines and Acceptable Birth Control Methods).

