Time to treatment failure is defined to be the time from registration to the date at which the patient is removed from treatment due to progression, adverse events, or refusal. If the patient is considered to be a major treatment violation or is taken off study as a non-protocol failure, the patient will be censored on the date they are removed from treatment.

Adverse Events: All eligible patients who began treatment will be considered evaluable for assessing adverse event rate(s). The maximum grade for each type of adverse event will be recorded for each patient, and frequency tables will be reviewed to determine patterns. Additionally, the relationship of the adverse event(s) to the study treatment will be taken into consideration. The duration of treatment, dose level and total dose per agent each cycle will also be summarized using descriptive statistics. Lastly, renal function over time will be described using descriptive statistics.

16.38 Pharmacokinetic Analysis:

Pharmacokinetic (PK) analysis will be performed in consented subjects administered a dose during the "Phase II" portion of the trial.

The following pharmacokinetic parameters will be determined using the non-compartmental methods:

- Maximum observed plasma concentration (C_{\max})
- Time to maximum plasma concentration (t_{\max})
- Area under the plasma concentration-time curve from Time 0 to the last measurable time point (AUC)

- Area under the plasma concentration-time curve from Time 0 to infinity (AUC_{∞})
- Apparent total body clearance when dosed orally (CL/F)
- Apparent volume of distribution when dosed orally (V_z/F)
- Terminal elimination half-life in plasma ($t_{1/2,z}$)

The relationship between renal function (CrCl) and PK parameters will be explored.

The results will be summarized by descriptive statistics.

16.4 Data & Safety Monitoring:

Study Monitoring: PrECOG, LLC will be responsible for study monitoring. Refer to Section 19.5 for details.

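### AUC to infinity is planned from a Day 6 multiple-dose profile with no dosing-interval AUC, so exposure is overstated by an amount that differs by renal group and schedule

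*Protocol*

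**What the plan says.** Footnote 6 of the Test Schedule (Protocol section 4.0) sets blood sampling "on Day 6 of Cycle 1: 0 (pre-dose), 0.5, 1, 1.5, 2, 3, 4, 6, 8, 24 hr at all dose groups", and additionally "at 48 and 72 hr for patients in Group B with severe renal impairment or in Group C on dialysis". SAP section 7 repeats this schedule. No other day is sampled. Section 1.4 says of lenalidomide: "Steady-state levels are achieved by Day 4".

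Section 16.38 lists the non-compartmental parameters: Cmax, tmax, AUC to the last measurable time, "Area under the plasma concentration-time curve from Time 0 to infinity", CL/F, Vz/F and terminal half-life. It gives no formula for CL/F, lists no AUC over a dosing interval and has no correction for the pre-dose concentration. It adds: "The relationship between renal function (CrCl) and PK parameters will be explored". SAP sections 2.1 and 8 leave PK analysis to a separate report.

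In Tables 7.211 to 7.213, Group A is dosed daily on Days 1-21, Group B every other day at levels 1 and 2 and daily at levels 3 and 4, and Group C daily at all current levels.

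**The concern.** AUC to infinity describes total exposure to a dose when no drug was present beforehand. For linear kinetics at steady state, the equivalent quantity is the AUC over one dosing interval. Extending a steady-state curve to infinity adds the remaining tails of all earlier doses. If clearance is then computed as dose over that area it is too low, and Vz/F with it.

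The statements in sections 1.3 and 1.4 that the drug does not accumulate do not settle the matter. Section 1.3 ties that finding to half-lives of 2.8-6.1 h, and section 1.4 ties it to the recommended regimen. Section 1.7 reports AUC increases of about 140%, 240% and 360% in moderate impairment, severe impairment and ESRD off dialysis, with Cmax unrelated to CrCl. Lower clearance at a similar volume means a longer half-life and more carry-over. At stake is the objective in section 2.24, PK in impaired renal function, and the CrCl relation in section 16.38: part of any relation found could come from carry-over rather than clearance.

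**Working it through.** **Inputs from the protocol.** Half-life 2.8-6.1 h with daily dosing (section 1.3; renal function of those patients not stated). AUC multiples of 2.4, 3.4 and 4.6, reading the increases in section 1.7 as increases by 140%, 240% and 360%. Interval tau of 24 h, or 48 h for Group B levels 1 and 2.

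**Check on that reading.** The doses listed in section 1.7 were derived to match 25 mg exposure in normal renal function. Average daily dose times multiple gives 10 x 2.4 = 24.0 (moderate), 7.5 x 3.4 = 25.5 (severe) and (15 x 3/7) x 4.6 = 29.6 (ESRD, before dialysis removal). Reading the figures as increases to 140%, 240% and 360% gives 14.0, 18.0 and 23.1, a poorer fit in the moderate and severe rows.

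**Assumptions not in the documents.** One compartment, linear kinetics, constant V/F (so half-life scales with AUC), absorption rate ka = 2 per hour, dialysis removal ignored.

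**Formula.** Let q = 2^(-tau/half-life), k = ln 2/half-life, and m the number of earlier doses (5 for daily dosing on Day 6; 2 for the third every-other-day dose). By superposition,

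R = AUC-infinity on the sampling day / single-dose AUC-infinity = 1 + [ka/(ka - k)] x (q + q^2 + ... + q^m).

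Dose/AUC-infinity is then the true CL/F divided by R, an understatement of 1 - 1/R.

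**The protocol's own statement first.** At half-lives of 2.8 and 6.1 h with tau = 24 h, R = 1.003 and 1.07. This agrees with no accumulation in those patients.

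**One case in full.** Group C, upper end: half-life 6.1 x 4.6 = 28.1 h, q = 0.553, sum of five powers = 1.172, ka/(ka - k) = 1.0125, so R = 1 + 1.0125 x 1.172 = 2.19 and 1 - 1/R = 54%.

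| Group and schedule | Half-life (h) | R | CL/F low by, if dose/AUC-infinity |
|---|---|---|---|
| A, daily | 6.7-14.6 | 1.10-1.48 | 9-33% |
| B, daily | 9.5-20.7 | 1.22-1.81 | 18-45% |
| B, every other day, from a dosing day | 9.5-20.7 | 1.03-1.25 | 3-20% |
| C, daily | 12.9-28.1 | 1.39-2.19 | 28-54% |

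**Interval AUC on the same profiles.** With daily dosing, AUC over 0-24 h on Day 6 is 0.97-1.00 of the single-dose AUC-infinity in all three groups. The 0.97 arises at a half-life of 28.1 h, where Day 6 is slightly short of steady state.

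**Sampling against dosing.**
- Every-other-day dosing from Day 1 falls on Days 1, 3, 5 and 7. Day 6 is not a dosing day, yet a pre-dose sample and a timed profile are planned for it.
- If daily dosing continues in Groups B and C, the 24, 48 and 72 h samples are all troughs. In a simulated non-compartmental analysis at the protocol's times (base half-lives 3-6.1 h), the terminal slope fitted to those three points is about zero, AUC-infinity cannot be estimated, and AUC to the last sample is 1.8-2.4 times the true single-dose value. The Group B and C daily rows of the table therefore apply only if later doses are withheld or samples after the next dose are left out. The documents state neither.

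**The case against.** The strongest reply is that the documents do not commit to the error in full. A reader might infer that clearance will certainly be understated. Section 16.38 gives no CL/F formula, and the separate PK report could use the interval AUC. That stands: dose over AUC-infinity is the natural reading of the list, but it is not stated. The inflation of AUC-infinity itself needs no formula.

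A reader might also infer that the bias is always largest where renal function is worst. The documents do not support this. If Group B enters phase II on an every-other-day level, its factor (1.03-1.25) is below Group A's with daily dosing at the same base half-life: 1.03 against 1.10 at 2.8 h, and 1.25 against 1.48 at 6.1 h.

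For Group A the last sample is at 24 h, so AUC to the last measurable time already equals AUC(0-24) if that level is measurable. This also stands, but it does not extend to Groups B and C, whose sampling runs to 72 h.

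Nor does section 16.38 plan a comparison with the single-dose renal study, although section 1.7 says the trial is designed after it.

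The sizes are soft. The moderate multiple is from CrCl 30-50 mL/min while Group A runs to 60, the ESRD multiple is off dialysis while Group C is dialysed, and some PK background is redacted.

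**Conclusion.** The point holds in a limited form. Section 16.38 plans an AUC to infinity that, from a Day 6 profile, includes carry-over, and it omits the interval AUC that would avoid this. Given linear kinetics, the direction follows from superposition alone. The sizes, about 1.1-1.5-fold, 1.2-1.8-fold and 1.4-2.2-fold in Groups A, B and C with daily dosing, rest on the assumptions listed in the working.

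The understatement of CL/F is conditional on the unstated formula. Because the bias differs by group and schedule it distorts the CrCl-PK relation, but it rises steadily with worse renal function only if all three groups are dosed daily.

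The analysis is a secondary objective in up to 12 patients, with at least two per group, and no trial decision depends on it. The primary endpoint is unaffected.

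**What to change.** In section 16.38, replace AUC to infinity with AUC over the dosing interval (AUC0-tau, with tau matched to the assigned schedule), computed only from samples taken before the next dose. State CL/F = dose/AUC0-tau and Vz/F = (CL/F)/lambda-z. Carry the same definitions into the separate PK report.

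For daily regimens this is a wording change, and the existing 0-24 h samples suffice. It should not be assumed that the same holds for every-other-day Group B: a 48 h window opened on Day 6 straddles the Day 7 dose and gives no clean interval profile.

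Separately, the sponsor should reconcile two sets of provisions: the Day 6 pre-dose sample in section 4.0 with the every-other-day levels in Table 7.212, and the 48 and 72 h samples with continued dosing in Groups B and C. How they are reconciled is for the sponsor to decide. The PK report should then say which samples precede the next dose.

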7.22 Definition of Dose-Limiting Adverse Events

Dose Limiting Adverse Events:

Dose Limiting Toxicity (DLT) will be defined as any of the following events that is determined to be possibly, probably, or definitely related to lenalidomide (as determined by the investigator) within the first cycle of therapy irrespective of whether the adverse events resolved:

- Grade 3 or higher neutropenia with fever $\geq 38.5^{\circ}\text{C}$
- Grade 4 neutropenia ≥ 7 days
- Grade 4 or higher thrombocytopenia
- Other non-hematologic Grade 4 or higher adverse event not present prior to starting therapy or not due to underlying cause

Management and dose modifications associated with the above AEs are outlined in Section 8.0.

7.23 Dose Escalation Phase:

A standard cohort of 3 phase I design will be used where subjects will be initially enrolled in groups of three and individually assessed for safety and DLT. For a subject to be considered evaluable for dose limiting toxicity the subject must have received at least one dose of both drugs in Cycle 1 and have not been withdrawn from the study prior to Cycle 2 secondary to a drug related AE. If a subject withdraws from the study without meeting these criteria for reasons other than adverse events, the subject will be replaced in that cohort.

Doses will be escalated until the first observation of a DLT as defined in Section 7.22 in the first treatment cycle in a group of at least 3 subjects treated at that dose level. All DLTs occurring in the first 3 cycles of the Phase I and II components will be collected and considered in the overall analysis, however, only DLTs occurring in Cycle 1 will define MTD during the Phase I component. Severity grading will be defined using National Cancer Institute Common Terminology Criteria for Adverse Events (NCI CTCAE V4.0). A one-time dose escalation of lenalidomide after 2 cycles of treatment due to improvement of renal function is allowed within an individual patient as described in Section 8.3.

A standard 3+3 phase I design will be used to determine the recommended dose in each renal dysfunction group. Dose level 1 will be the initial dose level (see Tables in Section 7.21).

- For current dose level accrue 3 patients (accrual for the group [Group A, B, or C] will be temporarily closed while the 3 patients are evaluated for DLT).
- If exactly 0/3 experience a DLT, then proceed to the next higher dose level.

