- If exactly 1/3 experience a DLT, then accrue 3 more patients at the current dose level (accrual for the group [Group A, B, or C] will be temporarily closed while the 3 additional patients are evaluated for DLT). If (out of 6 patients) there are at least 2 that experienced a DLT, the recommended dose level has been exceeded. Drop down one dose level.
- If 2 or more (out of 3) patients experience a DLT, the recommended dose level has been exceeded. Drop down one dose level.

The recommended dose level for the phase II portion of the trial is the maximum dose level that resulted in less than 2/6 patients with DLTs. Patients who experience DLTs will be dose reduced to the next lower dose level.

Dose escalation will proceed within each group [Group A, B, or C] according to the following scheme. A DLT is defined above.

Number of Patients with DLT at a Given Dose Level	Phase I Escalation Decision Rule
0 out of 3	Enter 3 patients at the next dose level.
≥ 2	Dose escalation will be stopped. This dose level will be declared the maximally administered dose (highest dose administered). Three (3) additional patients will be entered at the next lowest dose level if only 3 patients were treated previously at that dose.
1 out of 3	Enter at least 3 more patients at this dose level. 
 • If 0 of these 3 patients experience DLT, proceed to the next dose level. • If 1 or more of this group suffer DLT, then dose escalation is stopped, and this dose is declared the maximally administered dose. Three (3) additional patients will be entered at the next lowest dose level if only 3 patients were treated previously at that dose.
≤ 1 out of 6 at highest dose level below the maximally administered dose	This is generally the recommended phase 2 dose. At least 6 patients must be entered at the recommended phase 2 dose.

Once the MTD is reached in the Phase I component for Group A, B or C, the group with the defined MTD dose will immediately be eligible to go to the Phase II component, and will not have to wait for the MTD in the other two groups

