10.4 Serious Adverse Event Reporting by Investigator to PrECOG

10.41 Serious adverse events (SAE) are defined above. The investigator should inform PrECOG of any SAE within 24 hours of being aware of the event. The date of awareness should be noted on the report. This must be documented on PrECOG SAE form. This form must be completed and supplied to PrECOG within 24 hours/1 business day at the latest on the following working day. The initial report must be as complete as possible, including details of the current illness and (serious) adverse event, and an assessment of the causal relationship between the event and the investigational product(s). Information not available at the time of the initial report (e.g., an end date for the adverse event or laboratory values received after the report) must be documented on a follow-up PrECOG SAE report form. A final report to document resolution of the SAE is required. A copy of the fax transmission confirmation of the SAE report to PrECOG should be attached to the SAE and retained with the patient records.

PrECOG Drug Safety Contact Information

All SAEs should be faxed to:

[contact]

as per the instructions found in study materials provided to the investigator site.

████████████████████
Medical Monitor
During Normal Business Hours
8:30 am-5:00 pm EST
[contact]
After Normal Business Hours
[contact]
████████████████████

Manager, Clinical Safety
During Normal Business Hours
8:30 am-5:00 pm EST
[contact] ext 143
After Normal Business Hours
[contact]

PrECOG will notify Celgene of any SAE within 1 business day of receipt from the site.

Collection of complete information concerning SAEs is extremely important. Full descriptions of each event will be followed. Thus, follow-up information which becomes available as the SAE evolves, as well as supporting documentation (e.g., hospital discharge summaries and autopsy reports), should be collected subsequently, if not available at the time of the initial report, and immediately sent using the same procedure as the initial SAE report.

All SAEs must be collected which occur within 30 days of discontinuation of dosing for lenalidomide and/or dexamethasone, whichever is the last to be received. In addition, the Investigator should notify PrECOG or designee of any SAE that may occur after this time period which they believe to be definitely, probably or possibly related to investigational product.

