Adverse Event Stopping Rule: The stopping rule specified below is based on the knowledge available at study development. We note that the Adverse Event Stopping Rule may be adjusted in the event of either (1) the study re-opening to accrual or (2) at any time during the conduct of the trial and in consideration of newly acquired information regarding the adverse event profile of the treatment(s) under investigation. The study team may choose to suspend accrual because of unexpected adverse event profiles that have not crossed the specified rule below.

Accrual will be temporarily suspended to a group if at any time we observe events considered at least possibly related to study treatment (e.g., an adverse event with attribute specified as “possible”, “probable”, or “definite”) that satisfy the following:

- If 7 or more patients in the first 20 treated patients (or 33% of patients after 20 have been accrued) experience a grade 4 or higher non-hematologic adverse event.

We note that we will review grade 4 and 5 adverse events deemed “unrelated” or “unlikely to be related”, to verify their attribution and to monitor the emergence of a previously unrecognized treatment-related adverse event. The adverse event rule will be evaluated for each group using all patients in the group who initiate treatment (e.g., will include patients in the phase I and phase II components).

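### Section 16.4 sets no accrual pause for related deaths as such; a pause-and-review at the second related death in a group would be a cheap addition

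*Protocol*

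**What the plan says.** The Adverse Event Stopping Rule in Protocol 16.4 suspends accrual to a group when at least possibly related events meet this condition: "If 7 or more patients in the first 20 treated patients (or 33% of patients after 20 have been accrued) experience a grade 4" non-hematologic event or worse. The count runs within each group, over all treated patients of both phases. The SAP has no stopping rule.

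Other safeguards:

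- **Discretion (16.4).** "The study team may choose to suspend accrual because of unexpected adverse event profiles that have not crossed the specified rule below". The rule itself may also be adjusted during the trial.
- **Attribution review (16.4).** Grade 4 and 5 events judged unrelated or unlikely are reviewed "to verify their attribution and to monitor the emergence of a previously unrecognized treatment-related adverse event".
- **Phase I, Cycle 1 (7.22, 7.23).** Dose-limiting toxicities include some hematologic events, such as "Grade 4 or higher thrombocytopenia". Accrual to the group closes while each cohort of three is assessed; after one DLT in three, it "will be temporarily closed while the 3 additional patients are evaluated for DLT". However, "only DLTs occurring in Cycle 1 will define MTD during the Phase I component".
- **Later cycles and Phase II (7.23).** "All DLTs occurring in the first 3 cycles of the Phase I and II components will be collected and considered in the overall analysis". No accrual action is attached.
- **Reporting (10.4, 19.4).** Sites report SAEs within 24 hours, and "PrECOG will notify Celgene of any SAE within 1 business day of receipt from the site". Serious, unexpected, related events go to investigators, who forward them to their IRBs.

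**The concern.** The boundary measures total severe non-hematologic toxicity. It responds when that is high, but has no separate response to deaths. Six related non-hematologic deaths among a group's first 20 patients, or any number recorded under hematologic terms, would not by themselves require a pause. None of the other safeguards requires one after Cycle 1 or in Phase II.

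The setting makes this worth attention. Lenalidomide is renally excreted, and the groups extend to dialysis patients. Protocol 1.3 reports grade 3-4 thrombocytopenia in 18.8% of patients with creatinine clearance below 30 mL/min against 5.5% above it, so the excluded category is one where excess toxicity is already documented. The Phase II dose rests on Cycle 1 DLTs in about 6 patients per group, and 15 more per group then start at that dose. What is at stake is whether new patients keep entering a group after related deaths without a required review.

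**Working it through.** **The boundary.** 0.33 × 20 = 6.6, which rounds up to 7, so the count and the percentage agree. Later limits are 7 at n = 21, 10 at 30, 11 at 33 and 13 at 39. The protocol gives no operating characteristics for this rule. With X ~ Binomial(20, p), P(X ≥ 7) is 0.0024, 0.087, 0.39 and 0.75 at combined related grade 4-5 non-hematologic rates of 10%, 20%, 30% and 40%.

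**Inputs.** Protocol 16.11 gives 15 Phase II patients per group and implies expected group sizes of 30, 33 and 33 (15, 18 and 18 in Phase I, plus 15 each), total 96. Assumed: related-death rate d of 1%, 2%, 5% or 10%; non-fatal grade 4 events in another g = 10% of patients; independent patients; all deaths non-hematologic, so that they count.

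**Two or more related deaths, no mandatory suspension by 20 patients.** The total must stay at 6 or below, so

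P = Σ(j = 2..6) C(20, j) d^j × Σ(k = 0..6−j) C(20−j, k) g^k (1−d−g)^(20−j−k).

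**Two or more related deaths among n patients.** P = 1 − (1−d)^n − n d (1−d)^(n−1). For n = 15 and d = 0.05: 1 − 0.4633 − 0.3658 = 0.171.

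| Related-death rate | ≥2 deaths, no suspension, by 20 | ≥2 deaths in 20, any | ≥2 deaths in 15 Phase II patients |
|---|---|---|---|
| 1% | 1.6% | 1.7% | 1.0% |
| 2% | 5.8% | 6.0% | 3.5% |
| 5% | 24.8% | 26.4% | 17% |
| 10% | 52.6% | 60.8% | 45% |

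The second column is an upper bound for the gap, for two reasons. It includes Phase I Cycle 1 deaths, which the DLT rule already handles, and 15 to 18 of a group's first 20 patients are expected to be Phase I. It also treats each event as known before the next patient enrolls. If some deaths carried hematologic terms, the probability would move toward the third column and could not exceed it. The last column leaves out later-cycle deaths in Phase I patients, so it is not a complete measure either.

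A higher background of grade 4 events makes the boundary work better: at 10% deaths plus 20% others it fires with probability 39.2%, and the no-suspension probability falls to 29.6%.

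**Cost of a second-death trigger.** At least one pause in a 33-patient group: at 2%, 1 − 0.5134 − 0.3458 = 0.141. Expected reviews per group are n d − 1 + (1−d)^n; at 2% this is 0.145 for 30 patients and 0.173 for 33, so 0.145 + 2 × 0.173 ≈ 0.49 in all. Review length is an assumption, taken as 1 to 4 weeks.

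| Related-death rate | ≥1 pause in a 33-patient group | Expected reviews, 96 patients | Group-weeks at 1 to 4 weeks each |
|---|---|---|---|
| 1% | 4% | 0.14 | 0.1-0.5 |
| 2% | 14% | 0.49 | 0.5-2.0 |
| 5% | 50% | 2.4 | 2.4-9.5 |

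The group-weeks lean high, because a review after a group has filled delays no accrual.

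**The case against.** The strongest reply is that this is a preference. Section 16.4 joins a numeric boundary to stated discretion, every death reaches the sponsor within 24 hours, and a diligent team would pause unprompted. The proposal turns an existing power into a duty. That is fair, and it is why this is an improvement and not a correction. It does not remove the point: the discretionary clause is framed around unexpected adverse event profiles and does not single out a death.

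A reader might infer that every pause for a related death after Cycle 1 is discretionary. The text does not support that: a related non-hematologic death counts toward the 7, and if it crosses the boundary the pause is mandatory. A reader might also take 24.8% or 52.6% as the size of the gap. They are upper bounds at assumed rates, and at 1% or 2% the figures are small.

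Timing also limits the benefit. Protocol 16.13 plans 15 weeks of Phase II accrual per group, less than four 28-day cycles (16 weeks), so many later-cycle deaths would come after accrual has closed. A pause protects patients not yet enrolled, not those already on treatment.

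Finally, the one week that 16.13 allows for routine cohort evaluation may be short for a fatal event that needs discharge summaries or an autopsy report. Hence the range to 4 weeks.

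**Conclusion.** The point holds as a cheap improvement that should be made. That the mandatory rule pools grade 5 with grade 4 and leaves out hematologic terms follows from the text alone and needs no assumed rate. The size depends entirely on assumed rates: unimportant if related deaths occur in about 1% of patients, material at 5% or more. It would be wrong to conclude that the trial lacks protection against fatal toxicity. Cycle 1 of Phase I is covered by the DLT rule, reporting is prompt, and the study team can act below the boundary.

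**What to change.** Keep the 7-of-20 / 33% rule and add to Protocol 16.4:

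*The second and each later grade 5 event in a group that is at least possibly related to study treatment, hematologic or non-hematologic, in any cycle and either phase, suspends accrual to that group until the study chair, study statistician and medical monitor have completed and documented a review.*

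This is one sentence and uses existing roles and SAE reports. The price is the short pauses tabulated above, some for deaths later judged unrelated, since possible relatedness is a low threshold.

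A first-death trigger is a stricter option. At 1%, 2% and 5% it would pause a 33-patient group at least once with probability 28%, 49% and 82% (1 − (1−d)^33), with 0.96, 1.92 and 4.8 expected reviews over 96 patients (96 × d).
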